2.1. Trial design

The study is a two centre, open-label, uncontrolled single group phase 1A study of C19-A3 GNP peptide (10 µg peptide equivalent content) administered via Nanopass microneedles every 28 days for 8 weeks (3 doses), with follow-up for 12 weeks (20 weeks in total from first dose). Treatment will be given into the arm at a volume of 50ul. A schedule of study visits and procedures carried out at each study visit are shown in table 1.

2.2. Interim analysis and stopping guidance

2.2.1. No interim analysis planned

2.2.2. Guidelines for stopping a trial early

Injections and treatment will be immediately discontinued (but follow up will continue) in any subject who:

- Experiences a worsening local wheal or flare reaction at the injection site exceeding 5 cm.
- Experiences a serious adverse reaction or an allergic event suggestive of systemic hypersensitivity requiring more than local therapy (e.g. requiring steroids, bronchodilators, or adrenaline).
- Becomes pregnant

Data from these subjects will be included in the final analysis

If any individual in the study experiences a SUSAR, further dosing of all subjects at all sites will be suspended pending review by the Data Safety Monitoring Board (DSMB) and discussion with the CI and Sponsor. Advice will be sought from the DSMB regarding re-starting the study.

A substantial amendment application will be submitted to the Regulatory Agencies to resume the trial.

2.3. Timing of final analysis

Final statistical analysis should commence after the Statistical Analysis Plan (SAP) has been finalised and the study data locked. Prior to database lock, the SAP must be finalised and signed off by CI and Trial Statistician. All outcomes will be analysed collectively at the end of the trial and completed within the timeframe agreed by the study team.

Table 1: Schedule of study visits

| Visit number | Screening | | Pre V1 | Treatment | | | | | | Follow up | | | | |
|---|---|----|--|-----------|-------------------|--------------------------|----|----|-------------------|--------------------------|----|--------------------------------------|----|-------------------------------|
| | -2 | -1 | | 1 | 1b | 1C | 2 | 3 | 3b | 3C | 4 | Pre V5 | 5 | 6 |
| Weeks | These visits can be combined. | | A minimum of 72 hours prior to visit 1 | 0 | 1 day post visit1 | 3 to 5 days post visit 1 | 4 | 8 | 1 day post visit3 | 3 to 5 days post visit 3 | 9 | A | 14 | 20 |
| Days | Treatment must start within 3 months of screening commencing. | | | 0 | | | 28 | 56 | | | 63 | minimum of 72 hours prior to visit 5 | 98 | 140 (85 days post final dose) |
| Informed consent | X | | | | | | | | | | | | | |
| Study drug administration | | | | X | | | X | X | | | | | | |
| Follow up telephone call 24 hours post IMP | | | | X | | | X | X | | | | | X | |
| Physical Exam & ECG | X | | | X | | | X | X | | | | | X | |
| *Serum for AAbs and immune markers | | | | X | | | | X | | | | | X | |
| DRB1*0401 genotype | X | | | | | | | | | | | | | |
| MMTT | | | | X | | | | | | | | | X | |
| Urine c-peptide post meal | | X | | X | | | | | | | | | X | |
| 72 hour continuous glucose monitoring | | | Attach CGM | X | | | | | | | | Attach CGM | X | |
| Serum for Cystatin C | | | | X | | | | | | | X | | X | X |
| Urinalysis for blood, protein, and beta-2 microglobulin | | X | | X | | | X | | | | X | | X | X |
| Serum and urine (morning) sample to measure gold concentrations | | | | X | X* | | | | X* | | X | X | X | X |
| T cell (immune biomarker) assays (blood) | | | | X | | | | X | | | X | | X | |
| *LN aspiration 0/3-5d | | | | X | | X | X | | | X | | | | |
| *safety blood samples | | X | | X | | | X | | | | X | | X | X |
| HbA1c measurement | | X | | X | | | X | | | | X | | X | |
| Vital signs | X | X | | X | | | X | X | | | X | | X | X |
| Adverse Event assessment/con meds | | X | X | X | X | X | X | X | X | X | X | X | X | X |
| Urine pregnancy test | | X | | X | | | X | X | | | | | X | X |
| Record of insulin use | X | | | X | | | X | X | | | | | X | |
| *Blood glucose profile/insulin usage | | | | X | | | X | X | | | | | X | X |
| Assessment of glycaemic control/review blood sugar recordings | | | | X | | | X | X | | | | | X | |
| HFS survey | | | | X | | | | | | | | | X | |
| ADDOol | | | | X | | | | | | | | | X | |
| DTSQs | | | | X | | | | | | | | | X | |
| DTSQc | | | | | | | | | | | | | X | |

3. Study Population

8 subjects with a diagnosis of Type 1 diabetes will be included in the study. Autoimmune diabetes will be confirmed by measurement of islet cell autoantibodies. Patients will be required to possess the HLA-DR4 (B1*0401) genotype. Eligibility of patients will be reviewed according to the inclusion and exclusion criteria listed below.

3.1. Inclusion Criteria

- Clinical diagnosis of type 1 diabetes for > 3 months (dated from the first insulin injection).
- Commenced on insulin treatment within 1 month of diagnosis.
- Age 16 to 40 years
- 2 hour post-meal UCPCR > 0.53 nmol/mmol on at least one occasion (maximum 3 tests on different days)
- Possession of 0401 allele at the HLA-DRB1 gene locus
- Use of highly effective birth control methods with a failure rate of less than 1% per year when used consistently and correctly (for details, please refer to study protocol)
- Written and witnessed informed consent to participate.

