### **3.4 Sample size and population to be studied**

8 subjects aged 16 to 40 years with a diagnosis of Type 1 diabetes and some residual endogenous insulin (c-peptide) production will be included in the study. The Cardiff site will recruit subjects from the age of 18 years only and the Swedish site will recruit subjects from the age of 16 years, as the PI is an experienced paediatrician. Patients will be required to possess the HLA DRB1\*0401 genotype and residual c-peptide production as evidenced by a stimulated urine c-peptide: creatinine level > 0.2 nmol/mmol or random serum sample level

of > 60 pmol/l. Residual c-peptide production is required to be able to monitor for disease exacerbation (ie unexpectedly rapid loss of insulin c-peptide production).

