### 6.2 Inclusion criteria

1. Clinical diagnosis of type 1 diabetes for > 3 months (dated from the first insulin injection).
2. Commenced on insulin treatment within 1 month of diagnosis.
3. Age 16 to 40 years

4. 2 hour post-meal UCPCR > 0.2 nmol/mmol or random serum sample > 60 pmol/l on at least one occasion (maximum 3 tests on different days)
5. Possession of 0401 allele at the *HLA-DRB1* gene locus
6. The following birth control methods should be used (considered highly effective with a failure rate of less than 1% per year when used consistently and correctly):
  - combined (estrogen and progestogen containing) hormonal contraception associated with inhibition of ovulation:
    - oral
    - intravaginal
    - transdermal
  - progestogen-only hormonal contraception associated with inhibition of ovulation:
    - oral
    - injectable
    - implantable
  - \_intrauterine device (IUD)
  - \_intrauterine hormone-releasing system ( IUS)
  - \_bilateral tubal occlusion
  - \_vasectomised partner (provided that the partner is the sole sexual partner of the trial participant and that medical assessment of azoospermia has been confirmed)
  - Sexual abstinence (defined as refraining from heterosexual intercourse during the duration of the trial)
7. Written and witnessed informed consent to participate.

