4.2. Protocol deviations

Patients will be allowed to attend for follow up visit 4 (week 9) +/- 1 day of schedule, visit 5 (week 14), +/- 1 week of visit schedule and visit 6 (week 20) must be a minimum of 85 days post final dose/+2 weeks. Any visits outside of this guidance will be considered a protocol deviation.

All protocol violations and deviations as well as number of patients involved will be enumerated at the end of the study. A patient will be defined as being compliant with the protocol if s/he has taken all the three injections on target (within window) dates. Adherence to intervention will be enumerated according to treatment/followup on target (within window), protocol violations/deviations and missed dose/followup across the study schedule as set out in dummy table (ii) in Appendix 1.

Data from all enrolled patient will be included in analysis of safety as specified in section 5.1.1. and 5.3. Metabolic and immunological outcomes of patients who have missed or delayed dose/followup will also be explored with analysis specified in section 5.1.2

5. Analysis strategy

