|--------------|-----------|----------|-------------------|------------|-----------|------|----------------------|
| Screening No | Centre No | Visit No | HbA1c at Visit -1 | Serum Aabs | DRB1*0401 | A*02 | Pregnancy test (Y/N) |
|--------------|-----------|----------|-------------------|------------|-----------|------|----------------------|

Cont'd

| | | | |
|-----------------|--------------------------|----------------------|-----------------------|
| Urine C peptide | Albumin/creatinine ratio | Beta 2 microglobulin | Insulin cell free DNA |
|-----------------|--------------------------|----------------------|-----------------------|

KCL

- Table 4 shows the headings of the data file for assessing adherence to study intervention

| | | | | | | | |
|--------------|-----------|---------------|---------------|---------------|--------------|--------------|--------------|
| Screening No | Centre No | Visit 1 date* | Visit 2 date* | Visit 3 date* | Visit 4 date | Visit 5 date | Visit 6 date |
|--------------|-----------|---------------|---------------|---------------|--------------|--------------|--------------|

*Please flag up withdrawn patients or patients with treatment received date different from the visit date

- Endpoints Analysis (clinical observations)

Table 5 shows the headings of the data file for endpoints assessment with clinical observations

| | | | | | | | | |
|--------------|-----------|----------|-------|--------------|--------------|---------------------|--------------|----|
| Screening No | Centre No | Visit No | Rx No | Sbp (pre-Rx) | Dbp (pre-Rx) | Heart rate (pre-Rx) | T°C (pre-Rx) | Wt |
|--------------|-----------|----------|-------|--------------|--------------|---------------------|--------------|----|

Cont'd

| | | | | | | |
|---------------------|----------------------------------|--|--------------------------|--------------------------------|-----------------------------------|---|
| ECG performed (Y/N) | If N, separate list ¹ | If Y, (normal / abnormal, not sig/ abnormal and sig) | Phy exam performed (Y/N) | If N, list reason ² | If Y, Any system abnormal ? (Y/N) | If abnormal, separate list ³ |
|---------------------|----------------------------------|--|--------------------------|--------------------------------|-----------------------------------|---|

Cont'd

| | | | | | | |

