¹List reason for not performing ECG by subject and visit no in a separate spreadsheet. ²List reasons for not completing physical examination by subject and visit no in a separate spreadsheet. ³List all information about the abnormalities as captured in CRF by patient and visit no in a separate spreadsheet. ⁴List all clinically significant abnormalities as captured in CRF by patient and visit no in a separate spreadsheet. ⁵List changes in insulin as captured in the change of insulin log by patient in a separate spreadsheet. ⁶List concomitant medications as captured in concomitant medication log by patient in a separate spreadsheet. ⁷List reaction details as captured in post injection skin reaction log by patient and visit no in a separate spreadsheet. ⁸List whether the observation was judged to be clinically significant and whether it is an AE.

- Endpoints Analysis (laboratory assays)

Table 6 shows the headings of the data file for endpoints assessment with laboratory assays

For each of the analytes: eg GAD65

| | | | | |
|--------------|-----------|--------------|----------|----------|
| Screening No | Centre No | Treatment No | Visit -2 | Visit -1 |
|--------------|-----------|--------------|----------|----------|

Cont'd

| | | | | | |
|---------|---------|---------|---------|---------|---------|
| Visit 1 | Visit 2 | Visit 3 | Visit 4 | Visit 5 | Visit 6 |
|---------|---------|---------|---------|---------|---------|

For a full list of all the analytes, please refer to the Data Transferral Plan in Section 10 of the Data Management Plan

- Questionnaire Data

Table 7 shows the headings of the data file for endpoints assessment with questionnaire data

At Visit 1

| | | | | | | |
|--------------|-----------|----------|-------|------------|---------------|--------------|
| Screening No | Centre No | Visit No | Rx No | HFS items* | ADDQoL items* | DTSQs items* |
|--------------|-----------|----------|-------|------------|---------------|--------------|

Multiple columns

At Visit 5

| | | | | | | | |
|--------------|-----------|----------|-------|------------|---------------|--------------|--------------|
| Screening No | Centre No | Visit No | Rx No | HFS items* | ADDQoL items* | DTSQs items* | DTSQc items* |
|--------------|-----------|----------|-------|------------|---------------|--------------|--------------|

Multiple columns

- Safety data

Table 8 shows the headings of the data file for AE assessment

| | | | | | | | |

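### SAP and protocol disagree on the C-peptide entry criterion and the visit 4 window, and the protocol gives two end dates for AE collection; late safety data lack a planned summary

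*SAP*

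**What the plan says.** **C-peptide.** SAP 3.1 requires "2 hour post-meal UCPCR > 0.53 nmol/mmol on at least one occasion (maximum 3 tests on different days". SAP section 3 introduces its list with "Eligibility of patients will be reviewed according to the inclusion and exclusion criteria listed below". Protocol 6.2 has "2 hour post-meal UCPCR > 0.2 nmol/mmol or random serum sample > 60 pmol/l on at least one occasion", and protocol 3.4 agrees with it: "stimulated urine c-peptide: creatinine level > 0.2 nmol/mmol or random serum sample level" above 60 pmol/l. The screening laboratory file in SAP Appendix 2, Table 3 contains "Urine C peptide | Albumin/creatinine ratio | Beta 2 microglobulin | Insulin cell free DNA" but no serum C-peptide column. For the endpoint laboratory file (Table 6) the SAP says "For a full list of all the analytes, please refer to the Data Transferral Plan in Section 10 of the Data Management Plan"; that plan is not among the documents.

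**Visit 4.** SAP 4.2 states "Patients will be allowed to attend for follow up visit 4 (week 9) +/- 1 day of schedule". Protocol 5.4 and Table 1 keep the one-day tolerance but also let the visit be timed one week from the final injection. SAP 4.2 calls a patient "compliant with the protocol if s/he has taken all the three injections on target (within window) dates".

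**AE collection.** Protocol section 11 stops collection a month after whichever visit was the patient's last. Protocol 11.3 stops it a month after visit 6, week 20. Protocol 5.9.4 calls visit 7 the last visit and makes it optional. Table 1 schedules an AE assessment there.

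**Late safety data.** Protocol Table 1 schedules safety bloods, urinalysis, cystatin C and gold at visit 7. Protocol 6.15, 10.1 and 10.2 describe an optional patch test, which 10.2 says was added as a safety measure. SAP 5.3.1 to 5.3.3 end at week 20 or visit 6, and the SAP does not mention patch testing.

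**The concern.** AEs are the primary endpoint, so their collection period should have one definition. SAP 5.1.1 reports AEs as incidence per dose received. Under that measure a longer collection period can add events to the numerator while the denominator stays fixed.

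The other differences affect classification and reporting. A patient can satisfy the protocol's entry criterion and fail the list that the SAP names for reviewing eligibility. A visit 4 that satisfies the protocol can be recorded as a deviation. Hypersensitivity is part of the primary objective, yet the SAP's hypersensitivity analysis covers only reactions observed after injection. Any summary of the patch test or of the visit 7 laboratory data would therefore be chosen after the results are known.

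**Working it through.** **1. C-peptide criterion, side by side**

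| | Urine route | Serum route |
|---|---|---|
| Protocol 3.4, 6.2 | above 0.2 nmol/mmol | above 60 pmol/l |
| SAP 3.1 | above 0.53 nmol/mmol | none |

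The urine thresholds differ by a factor of 0.53/0.2 = 2.65. A patient with UCPCR above 0.2 and up to 0.53, or one who qualifies on serum only, meets the protocol and fails SAP 3.1. The documents give no distribution of UCPCR, so the number of such patients cannot be estimated. SAP 3.3 defines its populations by enrolment and by receipt of three injections, so neither population moves.

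**2. Visit 4 window**

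Inputs: dose interval 28 ± 3 days (protocol 5.4, SAP 4.1), visit tolerance ± 1 day, and nominal dose 3 on day 56. The plan's own figure reproduces: 56 + 7 = day 63.

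Let D be the day of dose 3. With both intervals in 25 to 31 days, D runs from 50 to 62. The post-injection window is D + 6 to D + 8. The SAP window is fixed at days 62 to 64.

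| D | Post-injection window | Shares a day with 62–64? |
|---|---|---|
| 50 | 56–58 | no |
| 53 | 59–61 | no |
| 54 | 60–62 | yes, day 62 |
| 56 | 62–64 | yes, all |
| 58 | 64–66 | yes, day 64 |
| 59 | 65–67 | no |
| 62 | 68–70 | no |

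The windows share no day when D is 50–53 or 59–62. Counting ordered interval pairs gives (1+2+3+4) + (4+3+2+1) = 20 of 7 × 7 = 49. The share of patients affected depends on an assumed interval distribution:

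- all pairs equally likely: 20/49 = 40.8%
- weights 1, 2, 3, 4, 3, 2, 1 on 25 to 31 days: 70/256 = 27.3%
- intervals uniform on 26 to 30 days: 6/25 = 24%
- intervals within 1 day of 28: 0/9 = 0%
- exact 28-day dosing: 0%, windows identical

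These figures count complete non-overlap. On D = 54, 55, 57 or 58 the overlap is partial, and a visit timed from the injection may still fall outside days 62–64. With 8 patients, one reclassified visit moves the visit 4 cell of adherence table (ii) by 1/8 = 12.5 percentage points.

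**3. AE end date**

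Taking a month as 4 weeks, for a visit 7 attender:

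- Protocol 11.3: 20 + 4 = week 24
- Protocol 11: 52 + 4 = week 56
- Difference: 56 − 24 = 32 weeks

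With a 30-day month the end dates are days 140 + 30 = 170 and 366 + 30 = 396, a gap of 226 days or 226/7 = 32.3 weeks. For a patient who stops at visit 6 the two rules agree.

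If 8 patients each receive 3 doses, the denominator is 24 person-doses. One AE captured only under the longer rule adds 1/24 = 0.042 per person-dose, with the denominator unchanged.

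**4. Visit 7 timing**

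Table 1 puts visit 7 at day 366, which is 366 − 56 = 310 days after the scheduled third dose. This is one day from the 311 stated in Table 1 and protocol 5.4. Protocol 10.1 instead places the late analysis 52 weeks, or 364 days, after the last dose. Table 1 evidently counts week 52 from the first dose.

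**The case against.** Much of this can be answered in part.

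- **Eligibility.** SAP Appendix 2, Table 1 takes eligibility as a yes/no flag, with failure reasons from the CRF. If the CRF follows the protocol, the SAP list may change nothing. That is a fair limit on the consequence, but the two lists still differ. A reader might infer that 0.53 is the wrong threshold, or that ineligible patients entered. The documents show only that the criteria conflict.
- **Visit 4.** The protocol asks for every effort to dose at 28 days, so 41% is not an expected rate. A visit on days 62–64 satisfies both documents whatever the day of dose 3. Both points stand. The effect is nevertheless wider than one table cell: SAP 4.2 also counts all deviations and explores outcomes in patients with delayed follow-up.
- **Visit 7 AEs.** A reader might infer that the SAP drops them. It does not: SAP 5.1.1 provides for AE review at every visit and for gathering all AEs, and the AE file has no visit cut-off. This does not settle the end date.
- **Late sampling.** A reader might infer that protocol 10.1 omits it. Its list of sampling times does stop at week 20 or visit 6, but the section then adds an optional late analysis. Only the timing wording conflicts.
- **Patch test.** Footnote 5 of Table 1 refers to subjects with a persistent reaction, while 6.15 speaks of patients given trial medication. The first group lies inside the second, so both statements can be true. The offer is unclear rather than contradictory.
- **Amendment route.** SAP 2.3 and section 8 allow correction before database lock. That makes the repair easy but does not make it unnecessary.

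**Conclusion.** The point holds in this form. The AE end date matters most because it concerns the primary endpoint: the two rules differ by about 32 weeks, but only for patients who attend optional visit 7. The C-peptide criteria conflict outright; the effect on reported eligibility is unknown. The visit 4 mismatch can turn a visit that meets the protocol into a SAP deviation. Its frequency ranges from 0% to 41% for complete non-overlap, and every figure in that range rests on an assumed interval distribution. It reaches adherence table (ii), the deviation count and the exploratory look at delayed follow-up. It does not reach the SAP's definition of a compliant patient or either analysis population.

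The missing summaries of visit 7 bloods, kidney markers and gold, and of the patch test, are a lesser point. On their own they would be closer to missing detail than to error. None of this invalidates the design.

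**What to change.** 1. Reconcile SAP 3.1 with protocol 3.4 and 6.2, without presuming which threshold is right, and record which criterion each patient met.
2. Carry the protocol's full visit 4 definition, including timing from the final injection, into SAP 4.2.
3. Reconcile protocol 11 with 11.3 and Table 1 so that AE collection has one end date.
4. Reconcile the visit 7 timing in protocol 10.1 with 5.4 and Table 1, and clarify between footnote 5 of Table 1 and section 6.15 who is offered the patch test.
5. Add to the SAP descriptive summaries of visit 7 laboratory, kidney and gold data and of patch-test results, with the number attending or tested as denominator.

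The cost is one SAP revision and a protocol clarification. It should not be assumed that data collection stays the same: settling the AE rule may lengthen or shorten collection for visit 7 attenders, and clarifying the patch-test offer may change who is tested. The late tables will describe attenders or tested patients only and should not be read as rates for all 8.

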3.2. Exclusion Criteria

- HbA1c > 86mmol/L (10%).
- Females who are pregnant, breast-feeding or not using adequate forms of contraception.
- Previous diagnosis of renal disease including glomerulonephritis or nephropathy.
- Raised serum creatinine or abnormal urine albumin/creatinine ratio (ACR) (values above the laboratory reference range). If the initial ACR is raised, this should be repeated on two further occasions as first morning samples. The subject can be included if both of these samples are negative (within the reference range).
- Use of immunosuppressive or immunomodulatory therapies, including systemic steroids within 1 month prior to receiving the IMP and any monoclonal antibody therapy given for any indication. Note that previous exposure to proinsulin peptide C19-A3 in a clinical trial is an exclusion criterion.
- Use of cannabis within one month prior to trial entry.
- Use of any hypoglycaemia agents other than insulin, for more than 6 weeks, at any time prior to trial entry.
- Use of inhaled insulin.
- Known alcohol abuse, drug abuse, HIV or hepatitis.
- Allergies to drug components or any excipients.
- Any other medical condition which, in the opinion of investigators, could affect the safety of the subject's participation or outcomes of the study, including immunocompromised states and autoimmune conditions.

- Subjects should not have had immunisations (flu and others) for 1 month prior to trial entry and should not receive any during their time in the trial – see section 5.6.
- Recent subject's involvement in other research studies which, in the opinion of investigators, may adversely affect the safety of the subjects or the results of the study.
- Abnormal ECG findings.

Number of patients screened and participated in the trial will be reported. Reasons for patients screened but not enrolled in the trial will be summarised. Baseline characteristics including but not restricted to age, gender, ethnicity, BMI, age of diagnosis and duration of diabetes of the enrolled and excluded patients will be summarised. The numeric variables will be summarised by mean and standard deviation. Both counts and percentages will be presented for the categorical variables. Baseline characteristics of the enrolled and the screened but not enrolled will be presented as set out in dummy table (i) in Appendix 1

